7.2.5 Efficacy analysis

Estimated GFR will be calculated using the CKD-EPI creatinine equation as described by (32). For French subjects, see [Section 10.5.3](#).

Annualized rate of change in eGFR during the placebo-controlled treatment period will be compared between lademirsen (SAR339375) and placebo using a linear mixed effect model. ATHENA Natural History Study (OBS16374) data will be used as prior information supplementing the placebo arm, using a Bayesian approach.

The model will include eGFR measurements from baseline to Week 48 as response variables, and it will include fix effects of treatment (lademirsen [SAR339375] or placebo), screening eGFR stratification factor, time, and treatment-by-time interaction. In addition, it will include random intercept and random slope for time to account for the between subject variability. Time will be treated as continuous variable based on actual eGFR assessment date relative to the randomization date.

A prior distribution for the slope of the placebo group was determined based on the annualized rate of change in eGFR observed in a subgroup of subjects from ATHENA Natural History Study, who are considered as rapid progressors meeting renal function criteria similar to I 05 in [Section 3.2.1](#). The prior distribution assumes a normal distribution for the slope of eGFR in the placebo group, with a mean of -10 and standard deviation of 2.22. Non-informative priors will be used for other parameters in the model. Efficacy of lademirsen (SAR339375) will be based on the posterior probability that the slope of the lademirsen (SAR339375) group is greater than the slope of the placebo group. A posterior probability of at least 95% will be considered significant.

The primary estimand will be the difference in mean slope of eGFR estimated from baseline to Week 48 in ITT population, regardless of whether or not subjects completed the study period of 48 weeks.

Change and percent change from baseline in eGFR at Week 24 and 48 will be analyzed using mixed effects model with repeated measures (MMRM), based on eGFR measurements up to Week 48.

The number and proportion of subjects who reach ESRD or initiation of hemodialysis or renal transplantation will be summarized by treatment group. The proportion will be estimated based on

total subjects in ITT population, as well as the Kaplan-Meier estimate taking consideration of lost to follow-up during the study.

Efficacy endpoints that include data from the open-label extension period will be summarized using descriptive statistics.

Exploratory analyses will be described in the statistical analysis plan finalized before database lock.

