7.2.1 Determination of sample size

An approximate 45 total subjects will be randomized in 2:1 ratio to lademirsen (SAR339375) versus placebo. The sample size will provide approximately 75% power to detect a reduced rate of decline of 5 mL/min/1.73 m²/year (~50% reduction) in eGFR annualized rate under lademirsen (SAR339375) treatment, in comparison to placebo.

Power calculations were based on simulations. The following model parameters were obtained from preliminary analysis of the ATHENA Natural History Study (OBS16374) data:

- Average linear decline in eGFR of 10 mL/min/1.73 m²/year in placebo arm
- Standard deviation (SD) for the residual error of eGFR of [REDACTED] mL/min/1.73 m² and SD for random effect of slope to be [REDACTED] mL/min/1.73 m²/year
- Mean and SD for intercept to be [REDACTED] mL/min/1.73 m² and [REDACTED] mL/min/1.73 m², respectively

In addition, power calculations were based on a success criterion defined in [Section 7.2.5](#) and a 10% dropout rate was assumed.

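### The approved protocol and the SAP specify different primary analyses: only the protocol uses a fixed ATHENA prior on the placebo slope, and its 75% power does not apply to the no-prior analysis

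*Protocol*

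**What the plan says.** Protocol 7.2.5 fits a linear mixed model to eGFR from baseline to Week 48. It supplements the placebo arm with a normal prior on the placebo slope "with a mean of -10 and standard deviation of 2.22. Non-informative priors will be used for other parameters in the model". The prior was derived from a rapid-progressor subgroup of the ATHENA natural history study, chosen by renal function criteria resembling I 05. The decision rule reads: "A posterior probability of at least 95% will be considered significant". Protocol 7.2.1 ties the sample size to that rule: "power calculations were based on a success criterion defined in" Section 7.2.5, and "The sample size will provide approximately 75% power to detect a reduced rate of decline of 5 mL/min/1.73 m²/year".

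SAP 4.3.2 specifies a random coefficient model fitted by restricted maximum likelihood. It uses no external prior and reports a slope difference with a 95% CI and p-value. SAP section 2 bases its power on a frequentist version of that model. The SAP addendum (section 3) keeps the statistical method for the final analysis, restricted to Stage 1. Addendum section 1 explains that SAP 2.0 was written for Amended Protocol 13, which was withdrawn from authority submission. It names Amendment 11, and Amendment 12 for France, as the latest approved versions. The protocol under review is Amendment 12.

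**The concern.** The approved protocol and the SAP define different primary analyses and different success rules, and the difference affects the result. The prior acts on one arm only. With non-informative priors on everything else, the lademirsen slope is in effect estimated from its own data, while the placebo slope is pulled toward -10. If placebo subjects in this trial decline more slowly than that, the pull makes placebo look worse than it is, and the gap counts as drug benefit. If they decline faster, the rule becomes conservative and loses power.

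The stated power has a related problem. It was simulated under the borrowing rule with the placebo slope placed exactly at the prior mean, so it says nothing about a 45-subject analysis without the prior.

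**Working it through.** **Inputs.** From Protocol 7.2.1: "An approximate 45 total subjects will be randomized in 2:1 ratio to lademirsen (SAR339375) versus placebo", so 30 and 15. Also "a 10% dropout rate was assumed", so 27 and 13.5 effective subjects if each arm loses 10%. The effect is 5 and the placebo assumption is "Average linear decline in eGFR of 10 mL/min/1.73 m²/year in placebo arm". From 7.2.5: prior SD 2.22 (variance 4.93) and a 95% threshold, z = 1.645. The residual SD and the slope SD are blacked out ("SD for random effect of slope to be [REDACTED] mL/min/1.73 m²/year"), so the 75% cannot be reproduced forward. As an assumption, both are replaced by one effective SD, s, of a subject's estimated slope, and s is solved from the 75%.

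**Formulas** (conjugate normal approximation).
- Vt = s²/nt and Vp = s²/np
- data weight w = (1/Vp) / (1/Vp + 1/2.22²)
- posterior variance of the difference D = Vt + 1/(1/Vp + 1/2.22²)
- P(success) = Φ{[δ + (1 − w)d − 1.645√D] / √(Vt + w²Vp)}, where δ is the true effect and d is how much slower than -10 the true placebo slope is.

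**Step 1, calibrate to 75%.** With δ = 5 and d = 0, s = 8.27 for 27/13.5 subjects, or 8.72 for 30/15. Check for 27/13.5: Vt = 2.54, Vp = 5.07, √D = √(2.54 + 2.50) = 2.24, and 1.645 × 2.24 = 3.69. The denominator is √(2.54 + 0.493² × 5.07) = 1.94. Then (5 − 3.69)/1.94 = 0.67 and Φ = 0.75.

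**Step 2, weight of the prior.** The placebo slope SE is √5.07 = 2.25 against a prior SD of 2.22, so the prior takes 51% of the weight. It is worth 8.27²/2.22² = 13.9 subjects beside 13.5 on placebo, or 15.4 beside 15 with the other calibration. For s from 5 to 12 the prior weight runs from 27% to 68%.

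**Step 3, false positives with no drug effect.** z = (0.507d − 3.69)/1.94.

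| True slope, both arms | z | Rate at s = 8.27 | Range, s = 5 to 12 |
|---|---|---|---|
| -12 | -2.42 | 0.8% | not computed |
| -10 | -1.90 | 2.9% | 2.7–3.6% |
| -9 | -1.64 | 5.0% | 5.0–5.5% |
| -8 | -1.38 | 8.4% | 8.1–8.4% |
| -7 | -1.12 | 13.2% | 11.5–13.4% |
| -5 | -0.60 | 27.6% | 21–29% |

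A Monte Carlo check with the SD treated as unknown (6,000 runs per point) gave 8.2–8.5% at -8 and 27–28% at -5. The spurious benefit at -5 is 0.507 × 5 = 2.5 mL/min/1.73 m²/year, half the effect the trial was sized for.

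**Step 4, power without the prior at the same s.** The SE of the difference is √(2.54 + 5.07) = 2.76, and 5/2.76 = 1.81. One-sided 5%: Φ(1.81 − 1.645) = 57%. Two-sided 5%: Φ(1.81 − 1.96) = 44%.

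**The case against.** The strongest reply is that the SAP has already removed the prior. The REML analysis in SAP 4.3.2, carried into the addendum, does not borrow, and the study was terminated after the first futility analysis. This stands. A reader might infer from the table that the trial's final analysis carries an 8% to 28% false-positive rate. The documents do not support that. The rates belong to the protocol's rule, and even there they need a true slope 2 to 5 units slower than -10.

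A second tempting reading is that slower decline is likely because I 05 also admits subjects on proteinuria, or as young men with reduced eGFR, without any slope requirement. That argument fails. The ATHENA subgroup was selected by criteria resembling I 05, which include those routes. Drift remains possible, since similar criteria are not identical and criterion A accepts slopes as slow as -4, but nothing in the documents points to a slope near -5.

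Third, the protocol's visible text does not claim a 5% type I error. It states a posterior-probability rule for a small Phase 2 study, so 5% is only the natural benchmark. Its section 7.2 is also described as a summary, and the text after 7.2.6 is blacked out. One can say that no down-weighting, conflict check or no-prior analysis is visible, but not that none exists.

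Finally, SAP section 2 gives its own power, 92.6%, and never relies on 75%. That is correct, but the figure is for 118 subjects across two stages. Stage 2 never enrolled, so neither stated power describes the analysis to be run on the 43 Stage 1 subjects.

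**Conclusion.** The concern holds as a mismatch between the approved protocol and the SAP, with a measurable difference between the two rules. Under the protocol rule the false-positive rate depends on where the true placebo slope lies. It is below 3% when decline is faster than -10 and passes 5% at about -9.

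The figures rest on the normal approximation, on one effective slope SD, and on reading the 75% as the power of the borrowing rule with no drift. Equal weighting of prior and placebo arm is therefore an inference, not a documented fact. The ends of the SD range (5 and 12) would imply 97% and 52% power under the protocol rule. SDs of 8 to 9 give 77% to 70%, with a prior weight of 49% to 55%. The false-positive rates at -9 and -8 hardly change across the whole range.

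The power finding is the one that bears on the planned analysis: at the SD that makes the protocol's 75% true, removing the prior costs about 18 points one-sided (75% − 57%) or 31 points two-sided (75% − 44%).

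**What to change.** Reconcile Protocol 7.2.5 and 7.2.1 with the SAP. Name the REML analysis without the prior as primary, state its success rule, and restate the power for that analysis and for the number of subjects it will use. If the Bayesian analysis is kept, pre-specify the vague-prior result beside it and report false-positive rates for a range of placebo slopes on both sides of -10. A robust mixture prior is one way to limit the drift, but it is a debatable design choice and is not needed for this correction.

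The cost is a wording change and one rerun of the power simulation. The downside is a lower stated power.

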7.2.6 Other analyses

PK, pharmacodynamic, and exploratory biomarker analyses (see [Section 10.5.2.2](#) for study conduct in China) will be described in the statistical analysis plan finalized before database lock. Measured plasma concentrations (observed PK parameters C_{max} and C_{trough}) for lademirsen (SAR339375), RG0005, and SUM (as applicable) will be summarized using descriptive statistics (eg, mean, standard deviation (SD), median, min-max, and coefficient of variation [%CV]).

The incidence and titer of ADA will be provided by treatment groups. Association between ADA status and safety may be explored.

[REDACTED]

8 DATA MANAGEMENT

8.1 DATA HANDLING

Data will be collected by means of eCRFs. The eCRF must be kept current to reflect subject status during the course of the study. A subject identification number will be used to identify the subject. Completion instructions will be provided.

The study will use an Internet-Based Remote Data Entry System or electronic data capture (EDC) system to collect the clinical trial data at the investigational sites. The system complies with 21 Code of Federal Regulations (CFR) Part 11 and International Conference on Harmonisation (ICH) E6 Good Clinical Practice (GCP). Queries are generally sent to the investigational site using an electronic data query system that provides an automatic audit trail of the corrections made by designated Investigator staff. All changes to the data have an electronic audit trail, in accordance with 21 CFR 11.10(e). Electronic signatures will be used in conformance with 21 CFR Part 11.

Source documents are to be retained to enable a reconstruction and evaluation of the trial. No original observations will be entered directly into the computerized system without source documentation. Laboratory data will be processed centrally.

Access to the EDC is controlled with user ID and password and can only be granted to appropriately trained users. Different types of users have different privileges assigned in the EDC system. A user access list is maintained throughout the study.

The Investigator will receive subject data for archiving at the investigational site following database lock.

8.2 DIRECT ACCESS TO SOURCE DATA/DOCUMENTS

The Investigator and institutions involved in this study will agree to allow study monitors from the Sponsor or its designee(s) direct access to all source data, CRFs, and documents, including a subject's complete medical record if necessary. Access must also be granted to authorized auditors, IRB/IEC reviewers, and all applicable regulatory bodies as necessary.

Source documents are considered to be all information in original records and certified copies of original records of clinical findings, observations, data, or other activities in a clinical study necessary for the reconstruction and evaluation of the study.

8.3 PROTECTION OF PERSONAL DATA

The completion of the study involves the collection and processing of personal data. All processing of personal data at the clinic and by the Sponsor must be carried out in accordance with national legislation concerning the protection of personal data.

The Investigator must ensure that the subject's privacy is maintained. On the CRF or other documents submitted to the Sponsor, subjects will be identified by a subject identification number only. Documents that are not submitted to the Sponsor (eg, signed ICFs) should be kept in a strictly confidential file by the Investigator.

As part of the required content of the ICF, subjects will be informed that their records may be reviewed by the Sponsor or its designee and by regulatory agencies. Should access to medical records require a separate waiver or authorization, it is the Investigator's responsibility to obtain such permission from the subject in writing before the subject is entered into the study.

8.4 CODING DICTIONARIES

Concomitant medications entered into the database will be coded using the most current World Health Organization Drug Dictionary, which employs the Anatomical Therapeutic Chemical classification system. Coexistent diseases and AEs will be coded using Medical Dictionary for Regulatory Activities (MedDRA).

8.5 DATABASE MANAGEMENT AND QUALITY CONTROL

Data queries will be reviewed by site and by data type to highlight any data issues that may be addressed through additional training or enhancements to the data validation programs.

A formal quality control review will also be conducted prior to database lock.

Any required changes to the database design and programming will be managed through a detailed change control process.

9 STUDY MANAGEMENT/PROCEDURES AND INSTRUCTIONS

9.1 SAFETY-RELATED PROCEDURES

9.1.1 Rapid notification on serious adverse events

All AEs that meet any seriousness criteria and AESI must be reported within 24 hours of awareness of the AE.

SAEs and complementary report forms will be reported via eCRF; any additional information will be reported to the contact address on the Sponsor Contact List.

The photocopy of all examinations carried out and the dates on which these examinations were performed should be reported to the representative of the monitoring team (refer to the Sponsor Contact List). Care should be taken to ensure that the subject's identity is protected and the subject's identifiers in the clinical trial are properly mentioned on any copy of source document provided to the Sponsor. For laboratory results, include the laboratory normal ranges.

Do not delay reporting SAEs. Investigators should not wait to receive additional information to fully document the event before reporting the SAE. The SAE report should provide the known information at the time of awareness that an SAE has occurred. A follow-up report should be sent when additional details are known.

All further data updates should be recorded in the eCRF as appropriate, and further documentation as well as additional information (for laboratory data, concomitant medication, subject status, etc) should be sent (by fax or e-mail) to the monitoring team within 24 hours of knowledge. In addition, any effort should be made to further document within the week (7 days) following initial notification any SAE that is fatal or life threatening.

A back-up plan is used (using paper flow) when the eCRF system does not work.

9.1.2 Dosing deviations

Over- or under-dosing are considered protocol deviations. The Investigator must notify Genzyme Corporation within 24 hours of any occurrence of overdose with study drug by telephone and by faxing/emailing a completed Protocol Deviation Form.

Symptomatic overdose (serious or non-serious) with IMP: In case of accidental or intentional overdose with the study treatment, even not fulfilling a seriousness criterion, is to be reported to the Sponsor immediately (within 24 hours) using the AE form together with the SAE complementary form to be entered in the eCRF.

Overdose is defined as increase of at least 30% above the intended dose at each administration or any two doses separated by <5 days.

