4.5 DOSE REDUCTION

Before administering each dose of study drug, the Investigator or delegate will review a subject's most recent safety data. A subject's platelet count will be obtained weekly before dose administration. Platelet counts will be measured from a central laboratory and can exceptionally be measured from a local laboratory. The most recent subject's platelet counts, but not older than 10 days, will be reviewed by the Investigator/physician before drug administration. Following the resolution of a Grade 2 AE or increase in aminotransferases (return to normal or \leq Grade 1 for AE) that does not otherwise trigger a stopping rule (see [Section 3.4](#)), the Investigator in consultation with the Sponsor Medical Manager may reduce an individual subject's dose to 110 mg Q2W. Dose reductions should be discussed with the Sponsor Medical Manger before implementation.

Grade 2 thrombocytopenia (platelet count from <100 000 to 50 000/microL) will result in suspension of dosing pending a return of platelet count to > LLN and review by the Investigator and the Sponsor Medical Manager. If dosing is to resume, it will be reduced to 110 mg Q2W.

For actions related to laboratory abnormalities that are indicative of potential hepatotoxicity, any subject experiencing a moderate (Grade 2) alkaline phosphatase, or bilirubin elevation will have a dose suspension and related laboratory test should be done weekly until the value(s) return to the normal range. For actions related to elevation of aminotransferases, please refer to [Section 10.3.2](#). If dosing is to resume, it will be reduced to 110 mg Q2W.

Injection site reactions will be graded according to [Table 6](#). Any Grade 2 (except erythema/redness) or Grade 3 ISR must have resolved or reached Grade 1 (“Mild”, eg, limited tenderness, and/or induration, except erythema/redness) prior to the next dose or subsequent dosing will be suspended. Consideration of resumed dosing at dose 110 mg Q2W will be based on review of the AE and time course to resolution in consultation with the Sponsor Medical Manager.

Once a subject’s dose has been reduced, it will not be increased.

For a regional or national emergency declared by a governmental agency, contingency measures are included in [Section 10.6](#).

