6.2.2 Adverse event of special interest

An adverse event of special interest (AESI) is an AE (serious or non-serious) of scientific and medical concern specific to the Sponsor's product or program, for which ongoing monitoring and immediate notification by the Investigator to the Sponsor is required. Such events may require further investigation in order to characterize and understand them. Adverse events of special interest may be added, modified or removed during a study by protocol amendment.

- Pregnancy of a female participant entered in a study as well as pregnancy occurring in a female partner of a male participant entered in a study with IMP:
 - Pregnancy occurring in a female participant entered in the clinical trial or in a female partner of a male participant entered in the clinical trial. It will be qualified as an SAE only if it fulfills one of the seriousness criteria (see Appendix 1 [[Section 10.1](#)]).

- In the event of pregnancy in a female participant, IMP should be discontinued.
- Follow-up of the pregnancy in a female participant or in a female partner of a male participant is mandatory until the outcome has been determined (see Appendix 4 [Section 10.4]).
- Symptomatic overdose (serious or non-serious) with IMP:
 - An overdose (accidental or intentional) with the IMP is an event suspected by the Investigator or spontaneously notified by the participant and defined as increase of at least 30% above the intended dose at each administration or any two doses separated by <5 days.
- Other specific AESIs subject to close monitoring:
 - All Grade ≥ 2 events listed in Table 3, except for eGFR
 - Grade ≥ 3 events of eGFR

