9.3 ADMINISTRATIVE PROCEDURES

9.3.1 Protocol amendment and protocol deviations

Protocol Amendment

Amendments to the protocol that entail corrections of typographical errors, clarifications of confusing wording, changes in study personnel, and minor modifications that have no impact on the safety of subjects or the conduct of the study will be classed as administrative amendments and will be submitted to the IRB/IECs and Regulatory Authorities for information only. The Sponsor (or designee) will ensure that acknowledgement is received and filed. Amendments that are classed as substantial amendments must be submitted to the appropriate Regulatory Authorities and the IRBs/IECs for approval.

Protocol Deviations

Should protocol deviations that affect a subject's safety occur, the Sponsor must be informed as soon as possible. Protocol deviations will be included in the Clinical Study Report. Reporting of protocol deviations to the IRB/IEC and in accordance with applicable Regulatory Authority mandates is an Investigator responsibility.

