10.3.2 Abnormal liver function

INCREASE IN AT (ALT or AST)

- In ANY CASE, FOLLOW** the instructions listed in the box below
1. **INFORM** the Site Monitor who will forward the information to the Study Manager
 2. **INVESTIGATE** specifically, for malaise with or without loss of consciousness, dizziness, and/or hypotension and/or episode of arrhythmia in the previous 72 hours; rule out muscular injury
 3. **PERFORM** the following tests:
 - LFTs: AST, ALT, alkaline phosphatase, total and conjugated bilirubin and prothrombin time / INR
 - CPK, serum creatinine, complete blood count
 - Anti-HAV IgM, anti-HBc IgM, (HBV-DNA if clinically indicated), anti-HCV and HCV RNA, anti CMV IgM and anti-HEV IgM antibodies
 - Depending on the clinical context, check for recent infection with EBV, herpes viruses, and toxoplasma
 - Hepatobiliary ultrasonography (or other imaging investigations if needed)
 4. **CONSIDER** Auto-antibodies: antinuclear, anti-DNA, anti-smooth muscle, anti-LKM
 5. **CONSIDER** consulting with hepatologist
 6. **CONSIDER** patient hospitalization if INR > 2 (or PT < 50%) and/or central nervous system disturbances suggesting hepatic encephalopathy
 7. **MONITOR LFTs after discontinuation of IMP:**
 - As closely as possible (or every 48 hours) until stabilization, then every 2 weeks until return to normal/baseline or clinical resolution

Notes: Upon resumption of study drug, transaminases and bilirubin should be assessed weekly for 4 weeks and the dose will be reduced to 110 mg Q2W. If a protocol-defined transaminase elevation interruption threshold recurs within 4 weeks of rechallenge with the study drug (with confirmation of the initial elevation by repeat testing within 48 to 72 hours), then the study drug must be permanently discontinued, regardless of the presumed etiology.

“Baseline” refers to ALT sampled at baseline visit; or if baseline value unavailable, to the latest ALT sampled before the baseline visit. The algorithm does not apply to the instances of increase in ALT during screening.

See Section 10.1 for guidance on safety reporting.

Normalization is defined as ≤ULN or baseline value, if baseline value is >ULN.

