4.5 Dose reduction	The text "or increase in aminotransferases" was added to the following sentence in the first paragraph: "The most recent subject's platelet counts, but not older than 10 days, will be reviewed by the Investigator/physician before drug administration. Following the resolution of a Grade 2 AE (return to normal or \leq Grade 1 for AE) that does not otherwise trigger a stopping rule (see Section 3.4), ...". In addition, the word "transaminase" was removed from the first sentence of the third paragraph, and a sentence with link to Section 10.3.2 was added in the third paragraph for further information about aminotransferases.	In accordance with the new guidance for management of elevated aminotransferases (Section 10.3.2).
	The abbreviation "AE" was removed from the second sentence in the paragraph beginning "Injection Site Reactions (ISRs)...".	Minor clarification that the paragraph is about ISRs, and not other adverse events.
5.4 Early termination	The clarification "(double-blind placebo or open-label extension periods)" was added to the first sentence.	Clarification of the treatment period.

Section # and Name	Description of Change	Brief Rationale
5.5 Follow-up period	The first sentence was revised to refer to subjects "who discontinue early and have completed the early termination visit" instead of referring to subjects who complete the double-blind period but who do not continue to the open-label period. In addition, "Week 48" and "of the double-blind part" were removed from the parenthesis in the first paragraph.	For clarification regarding the procedure for advancing to the follow-up period.
6.2.2 Adverse event of special interest And 9.1.2 Dosing deviations	The definition of overdose was updated: the timeframe between two doses was revised from ≤ 5 days to < 5 days.	Clarification for consistency with the allowed visit window (5-9 days).
6.2.3 Adverse events grading	Footnote b was added to Table 3.	For guidance in the event of elevated aminotransferases.
6.2.8 Regulatory reporting requirements for SAEs	The section was retitled from "Sponsor obligation" in the prior version, and all prior content except the 3 rd bullet in the current version were removed. The rest of the content was added for the current version.	The deleted information is duplicated in Section 9.2.5 and/or did not align to current Sanofi standard wording.

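### The overdose definition's only interval test (<5 days) fits weekly dosing, so a repeat injection at 5-9 days in a subject reduced to Q2W is not classed as an overdose

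*Protocol*

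**What the plan says.** Protocol Section 9.1.2 gives overdose two limbs, one on amount and one on interval: "Overdose is defined as increase of at least 30% above the intended dose at each administration or any two doses separated by <5 days". Section 6.2.2 repeats the interval limb ("any two doses separated by <5 days") when it makes symptomatic overdose an AESI.

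The classification has a reporting consequence. Under Section 9.1.2, "The Investigator must notify Genzyme Corporation within 24 hours of any occurrence of overdose with study drug". Symptomatic overdose, serious or not, also goes to the sponsor within 24 hours on the AE form with the SAE complementary form.

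The amendment history (Section 10.8.2, Amended Protocol 10) records that the cut-off moved from ≤5 to <5 days, and gives the reason: "Clarification for consistency with the allowed visit window (5-9 days").

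Individual dose reduction changes the frequency and leaves the injected amount alone. Section 4.5 says, for Grade 2 thrombocytopenia and for liver test elevations, "If dosing is to resume, it will be reduced to 110 mg Q2W". Section 10.3.2 says that on resumption after an aminotransferase rise "the dose will be reduced to 110 mg Q2W". Section 4.5 also offers Q2W after certain injection site reactions, and Section 4.2 carries a blinded-period reduction into the open-label period.

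Dosing errors outside the overdose definition are not ignored. Section 9.1.2 says "Over- or under-dosing are considered protocol deviations", and Section 9.3.1 adds "Should protocol deviations that affect a subject's safety occur, the Sponsor must be informed as soon as possible".

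SAP Section 4.7.1.2 describes dose reduction as a move from weekly to bi-weekly administration. Its under-planned percentage names omitted doses. Its above-planned percentage refers to administrations at a higher dose level than planned and does not mention surplus ones.

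**The concern.** The interval limb was set for the weekly schedule and has no counterpart for the schedule that reduced subjects follow. Those subjects were reduced for tolerability: platelets, liver tests or injection site reactions. They are the group in which an unplanned extra injection most needs prompt attention, and for them the definition does not recognise it.

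The error is plausible. Reduced subjects still have weekly blood counts. Table 1 and the visit lists in Section 5.2 show study drug every week with no Q2W note, and Section 5.3 describes the extension as weekly for everyone, with the Q2W exception stated elsewhere (Section 4.2 and the Synopsis).

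What is at stake is speed and route of reporting: the fixed 24-hour notice and, if there are symptoms, the overdose AESI report.

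**Working it through.** No power or sample-size figure is involved. The check is interval arithmetic plus a reading of each limb.

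**Inputs.** Weekly visits with a ±2 day window (Table 1, footnote b); overdose limbs of at least 30% above the intended dose or a gap under 5 days (Sections 6.2.2 and 9.1.2); reduced regimen of 110 mg Q2W (Sections 4.5 and 10.3.2).

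**Reproducing the plan's figure.** Weekly window = 7 ± 2 = 5 to 9 days. The lower edge is 7 − 2 = 5, which gives the <5 day limb and agrees with the reason in the amendment history.

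**Applying the limbs to a Q2W subject injected with 110 mg 5-9 days after the last dose.**
- Amount limb: 110/110 − 1 = 0%, below the 30% required.
- Interval limb: the shortest gap in the range is 5 days, and 5 is not less than 5. Not met.
- Exposure with a gap of 7 days: 2 × 110 = 220 mg in 14 days against 110 mg intended; 220/110 − 1 = 100% above.

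Neither limb is met although two-week exposure has doubled.

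**What a Q2W cut-off would be.** The documents state no Q2W window, so each value rests on an assumption.
- Same 2-day window: 14 − 2 = 12, so <12 days.
- Proportional to the weekly rule: 14 × 5/7 = 10, so <10 days.
- Two visits each shifting by 2 days independently: 14 − 4 = 10, so <10 days. The same logic applied to weekly dosing gives 7 − 4 = 3, not the plan's 5, so it is not the logic the protocol used.

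Both <10 and <12 cover gaps of 5-9 days. On the 2-day window assumption the uncovered range under the current text is wider, from 5 to just under 12 days.

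**SAP counts, assuming reduction at Week 24.** Planned double-blind doses are 24 weekly (Weeks 0-23) plus 12 at Q2W (Weeks 24-46), or 36. Add one surplus 110 mg dose.
- Above-planned: 0/36 = 0% if the comparison is of dose level at an administration; 1/36 = 2.8% if nothing planned in the off-week is read as a planned level of zero.
- Compliance: 36/36 = 100% if the surplus dose is not counted as compliant; 37/36 = 102.8% if it is.

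The text does not settle which reading applies.

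**The case against.** The strongest reply is that an overdose threshold is the sponsor's choice. 110 mg weekly is the study's full assigned dose, supported by the margins in Section 1.2.3, and 220 mg weekly for five doses was given to healthy volunteers (Section 1.1.4.2). A fixed cut-off could reasonably flag exposure above the maximum regimen and leave a missed individual schedule as a deviation. This stands in part, but those data do not address subjects already reduced for toxicity, and the recorded reason for 5 days refers only to the weekly window.

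It can also be argued that the intended dose in an off-week is zero, so the amount limb applies. That fails: the limb compares amounts at each administration, and if it caught off-schedule injections the interval limb would be redundant.

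The safeguards are substantial. Platelets are taken weekly and reviewed before dosing (Sections 4.5 and 6.2.15). Home and self-administered doses need confirmation from the investigator or delegate (Section 4.4). Grade 2 or higher platelet, aminotransferase, alkaline phosphatase and total bilirubin events are AESIs reportable within 24 hours (Sections 6.2.2 and 9.1.1). Exposure is listed by participant (SAP Section 4.7.1.2). These limit the consequence without replacing the notice. Section 9.3.1 depends on a judgment that safety is affected. Injection site reactions can lead to Q2W but are not in Table 3, so a non-serious one after an early injection has no other AESI route.

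A reader might infer that one early injection puts the subject back on the weekly regimen. It does not: it is one extra dose, and resumed weekly dosing would need the pre-dose check to fail repeatedly. A reader might also infer that the SAP certainly scores a surplus dose as nothing above plan. The wording is ambiguous, the measure is descriptive, and SAP Version 2.0 was written for Amended Protocol 13, whose overdose text is not among these documents.

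**Conclusion.** The gap is real and narrow. Under the current text, a 110 mg injection 5-9 days after the last dose in a subject reduced to Q2W is a protocol deviation and not an overdose. What is lost is the fixed 24-hour notice and, if symptomatic, the overdose AESI report. The event is not invisible, and no efficacy result changes.

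The classification follows directly from the definition and needs no assumption beyond reading the amount limb per administration. The assumptions enter only in choosing a Q2W cut-off and in the SAP example. The documents do not give the number of reduced subjects, so the frequency of such errors cannot be estimated. The SAP addendum records that the study was terminated after the first futility analysis, so the protocol clause now matters mainly if this text is reused. This is a cheap improvement to consider, not a defect that threatens the trial.

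**What to change.** In Sections 6.2.2 and 9.1.2, tie the interval limb to the assigned schedule: two doses less than 5 days apart for subjects on QW, or less than 12 days apart for subjects reduced to Q2W. The 12 applies the 2-day logic behind the existing 5 and should be accompanied by a stated Q2W window, because the protocol has none. If the sponsor prefers <10 days, that also covers the 5-9 day gap.

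As an optional clarification, add to the above-planned definition in SAP Section 4.7.1.2 that it includes doses administered outside the assigned schedule, to match the explicit mention of omitted doses in the under-planned definition.

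The cost is one clause in two protocol sections and one SAP line. No new data are needed, because exposure is already recorded and listed by participant. The downside is a few more overdose reports, including some gaps of 10 or 11 days that arise from scheduling.
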